This efficacy endpoint will be analyzed using a mixed model of repeated measures (MMRM) with Hb baseline value as covariate and treatment group and randomization stratification factors as fixed effects and MI ANCOVA as sensitivity analysis for Ex-US submission.

This null hypothesis will be rejected if the two-sided 95% CI for the difference of least square means from the mixed model is above -0.75 g/dL.

Hb values under the influence of a rescue therapy within 6 weeks prior to and during this 8-week evaluation period will be censored in the analysis.

- The average monthly iron use will be compared between the 2 treatment groups using an ANCOVA model with baseline iron replete as a covariate, and treatment group and randomization stratification factors as fixed effects. Superiority will be declared if the lower bound of the two-sided 95% CI of the difference between epoetin alfa and roxadustat exceeds zero.
- Mean change from baseline in LDL cholesterol averaged over Weeks 12 to 24 will be analyzed using an MMRM model with baseline LDL cholesterol as a covariate and treatment group, visit, visits by treatment arm, and randomization stratification factors as fixed effects. Superiority will be declared if the lower bound of the two-sided 95% CI of the difference between epoetin alfa and roxadustat exceeds zero.

- Proportion of subjects with exacerbation of hypertension, meeting at least 1 of the following criteria will be analyzed using CMH model adjusting for treatment group and stratification factors
  - Increase in blood pressure: An increase from baseline in systolic blood pressure (sBP) of  $\geq 20$  mm Hg and sBP  $> 170$  mmHg or an increase from baseline in diastolic blood pressure (dBP) of  $\geq 15$  mm Hg and dBP  $> 100$  mmHg. Increases from baseline in blood pressure must be confirmed by repeat measurement.

Noninferiority of roxadustat vs. epoetin alfa will be tested. Non-inferiority will be declared if the upper bound of the two-sided 95% CI of the hazard ratio is less than 1.3.

- Time to an increase in blood pressure (defined as an increase from baseline of  $\geq 20$  mm Hg systolic BP and sBP  $> 170$  mmHg or an increase from baseline of  $\geq 15$  mm Hg diastolic BP and dBP  $> 100$  mmHg). Time to an increase in blood pressure will be analyzed using the Cox Proportional Hazards model adjusting for treatment group and randomization stratification factors. Superiority of roxadustat vs. epoetin alfa will be tested.

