- Mean change in mean arterial pressure (MAP) averaged over Weeks 8 to 12 will be analyzed using an MMRM model with baseline MAP as a covariate and treatment group, visit, visits by treatment arm, and randomization stratification factors as factors. Superiority will be declared if the lower bound of the two-sided 95% CI of the difference between epoetin alfa and roxadustat exceeds zero.

The time to achieve the first Hb response defined as the primary endpoint (for ex-US submission) will be analyzed using the Cox Proportional Hazards model adjusting for treatment group and other stratification factors. Non-inferiority of roxadustat vs. epoetin alfa will be tested. Non-inferiority will be declared if the upper bound of the two-sided 95% CI of the hazard ratio is less than 1.3.

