3 STUDY DESIGN

This is a Phase 3, multicenter, randomized, open-label, and active-controlled study to evaluate the efficacy and safety of roxadustat in incident dialysis subjects with anemia.

A total of up to 1,200 subjects are planned to be randomized to receive roxadustat or epoetin alfa (active control) in a 1:1 ratio, respectively.

Randomization stratification factors include geographical region (US vs. Ex-US), screening Hb values (≤ 8 g/dL vs. >8 g/dL), and cardiovascular/cerebrovascular/thromboembolic medical history (yes vs. no).

In addition, the change of protocol were incorporated via amendments on 20 Oct 2014, 24 Nov 2015, 12 Aug 2016, and current one on 20 September 2017.

Subjects randomized to roxadustat will have doses administered thrice weekly (TIW) throughout the Treatment Period using an initial tiered, weight-based, dosing scheme (see Table 1 below), followed by dose titration every 4 weeks.

Table 1. Initial Study Drug Dosing

Study Drug (Dose Frequency)	Low Weight/Dose	Median Weight/Dose	High Weight/Dose
Roxadustat (TIW) – Original Protocol	45 to 60 kg/70 mg	>60 to 90 kg/100 mg	>90 to 160 kg/150 mg
Roxadustat (TIW) – Amended Protocol	≤ 70 kg/70 mg		>70 to 160 kg/100 mg
Epoetin alfa HD (TIW)	IV dosing according to epoetin alfa USPI or SmPC		
Epoetin alfa PD (TIW)	Epoetin alfa should be administered according to epoetin alfa USPI or SmPC or local standard care.		
	Abbreviations: HD = hemodialysis; IV = intravenous; PD = peritoneal dialysis; SmPC = summary of product characteristics; TIW = three times a week; USPI = United States Package Insert; wt = weight. Note: Weight in HD subjects = subject's dry weight.		

The study periods are as follows:

- Screening Period: Up to 6 weeks
- Treatment Period: Treatment duration is variable for individual subjects with maximum treatment duration of up to approximately 3 years after the last subject is randomized. The minimum treatment duration may be less than 52 weeks.
- Post-Treatment Follow-Up Period: 4 weeks

Dose Adjustments

Roxadustat arm

Dose adjustments will occur in two separate study dosing phases: the Correction Phase and the Maintenance Phase. Each of these phases will follow unique dose adjustment rules according to Appendix 2 in the amended protocol of 20 October 2014. All subjects in the roxadustat arm will be dosed orally TIW during the Treatment Period. The maximum roxadustat dose is 3.0 mg/kg per dose or 400 mg, whichever is lower.

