5.4 ADDITIONAL DATA HANDLING RULES AND PRESENTATION SPECIFICATIONS

The following general guidelines will apply to all statistical analyses and data presentations:

- Baseline is defined as the last available value obtained prior to the first dose of study drug, unless otherwise specified in this SAP.
- Hb baseline is defined as the mean of the at least last three available values obtained prior to the first dose.
- Baselines for reticulocyte count, reticulocyte hemoglobin content (CHr), hepcidin, serum iron parameters (transferring, TIBC, TSAT, Ferritin, sTfR, and iron), lipids, blood pressures and heart rate are defined as the mean of values obtained within 6 weeks prior to the first dose.
- Randomization stratification factors and enrollment protocol version derived from actual data (not the ones from the randomization system) will be used in all applicable analysis models.

The stratification factors to be used in efficacy analyses are:

1. Us vs Ex-US Screening Hb values (≤ 8 g/dL vs. > 8 g/dL) (other than Hb related endpoints)
2. Cardiovascular/cerebrovascular/thromboembolic medical history (Yes vs. No)
3. Geographic Region
4. The original protocol and amended protocols

- Unscheduled visits within an allowable window will be grouped into the closest scheduled visits based on the visit window specified in Appendix 1. For subjects who have more than one measurement at a certain scheduled visit, the last measurements

will be used, with the exception of CPK, WBC, liver function tests (i.e., ALT, AST, GGT, ALP, and total bilirubin), in which the maximum measurement will be used.

- By default, US conventional units will be used for laboratory value presentations. A set of lab summary tables in SI units will also be provided based on TLF index.
- Age is calculated as of date that the informed consent form was signed.
 - age = INTCK('YEAR', Birth date, date of Informed Consent, 'C') where INTCK is a SAS function.
- Duration of treatment or days in treatment is calculated as: last dose date – first dose date +1
- Body weight, height and temperatures will be converted using the following formula:
 - kg = lb/2.2
 - cm = 2.54 x in
 - C° = (5/9) x (F° – 32)
- The mean, standard deviation and median will be presented with adding one more decimal to raw data with rounding off. The minimum and maximum will be presented with the same number of decimals as in the raw data.

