11.2.1.4 Average monthly IV iron use during 28 to 52 Weeks

The average monthly IV iron use during the treatment period will be calculated for monthly intervals. The treatment period will be divided in periods of 28 days and for each of these periods the monthly mean of IV iron will be used using the following formula:

Monthly iron use for each subject = Total IV iron in mg / [(last visit date – first drug date +1)/ 28]

The average monthly iron use will be compared between the 2 treatment groups using an ANCOVA model adjust for baseline iron replete, treatment group and above-mentioned stratification factors as fixed effects. Superiority will be declared if the lower bound of the 2-

sided 95% confidence interval of the difference between Epoetin alfa and roxadustat exceeds 0.

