11.2.1.5 Mean change in mean arterial pressure (MAP) averaged over Weeks 8-12

Mean Arterial Pressure (MAP) will be calculated for each subject using the following formula: $MAP = (2/3) * DBP + (1/3) * SBP$.

Mean change from baseline in MAP will be analyzed and compared between the 2 treatment groups using an MMRM model with baseline MAP as a covariate, treatment group, visit, interaction of visit and treatment group, and above-mentioned stratification factors as fixed effects. The same strategy as that used in MMRM for Hb will be used to choose variance covariance structure. Data up to visit of Week 52 will be included in the model. The estimates for difference of MAP averaged over Weeks 8 to 12 between the two treatment groups will be generated from an estimate statement from Visit Week 8 to 12. Non-inferiority margin for the difference between groups is 1mmHg. Superiority will be declared if the upper bound of the 2-sided 95% confidence interval of the difference between roxadustat and ESA (roxadustat – ESA) is below 0.

11.2.1.6 Time to first exacerbation of hypertension over Week 28 to 52

Subject with exacerbation of hypertension is defined as meeting the following criterion:

Increase in blood pressure: An increase from baseline of ≥ 20 mm Hg systolic BP and sBP ≥ 170 mmHg or an increase from baseline of ≥ 15 mm Hg diastolic BP and dBP ≥ 100 mmHg. Increases from baseline in blood pressure are considered as confirmed by taking the mean of triplicates.

An exacerbation of hypertension is defined as an increase from baseline of ≥ 20 mm Hg systolic BP and sBP > 170 mmHg or an increase from baseline of ≥ 15 mm Hg diastolic BP and dBP > 100 mmHg).

Time to an exacerbation of hypertension in blood pressure will be analyzed and compared between the 2 treatment groups using the Cox Proportional Hazards model adjusting for baseline stratification factors. Both Non-inferiority and Superiority of roxadustat vs. ESA will be tested. The Non-inferiority margin for the difference between groups is 1.3 and the superiority margin for the difference between groups is 1. Subjects will be censored at the time of the last available blood pressure if an increase in blood pressure does not occur.

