11.3.6 Blood Pressure Effect

- Proportion of subjects achieving blood pressure treatment goal in ESRD subjects (pre dialysis systolic BP <140 mmHg systolic and diastolic BP<90 mmHg) averaged over Weeks 12-28. The proportion of subjects achieving blood pressure goal will be compared between the 2 treatment groups using logistic regression model adjusting for baseline pre dialysis systolic and pre dialysis diastolic blood pressures as covariates and baseline stratification factors as fixed effects.
- Mean change in mean arterial pressure (MAP) averaged over Weeks 20-28

The same analysis as 11.2.1.5 will be performed for the above endpoint.

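### The Cox model for time to a blood-pressure increase leaves out baseline blood pressure, so a valid test gives up a modest amount of power

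*Protocol*

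**What the plan says.** Protocol 8.4.3.2: "Time to an increase in blood pressure will be analyzed using the Cox Proportional Hazards model adjusting for treatment group and randomization stratification factors". The comparison is for superiority, and MAP and time to first Hb response follow it in the sequence.

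SAP 11.2.1.6 analyses time to first exacerbation of hypertension over Weeks 28-52 "using the Cox Proportional Hazards model adjusting for baseline stratification factors", for both non-inferiority and superiority. It is the last row of SAP Table 5.

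The factors are set in SAP section 3: "Randomization stratification factors include geographical region (US vs. Ex-US), screening Hb values", plus cardiovascular, cerebrovascular or thromboembolic history. SAP 5.4 adds protocol version. Blood pressure is not among them, and neither document adds it to this model elsewhere.

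SAP 11.2.1.6 gives the systolic limb of the event: "An exacerbation of hypertension is defined as an increase from baseline of ≥ 20 mm Hg systolic BP and sBP > 170 mmHg". The alternative diastolic limb there is a rise of at least 15 with a level above 100.

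Baseline pressure is taken at both screening visits and on Day 1 (Protocol 6.1.1 and 6.1.2.1) and is defined in SAP 5.4: "lipids, blood pressures and heart rate are defined as the mean of values obtained within 6 weeks prior to the first dose". Two other blood-pressure analyses use it. In Protocol 8.4.3.2 the MAP change "will be analyzed using an MMRM model with baseline MAP as a covariate", and SAP 11.3.6 compares attainment of the pressure goal with a "logistic regression model adjusting for baseline pre dialysis systolic and pre dialysis diastolic blood pressures as covariates".

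**The concern.** The event rule combines a fixed ceiling with a change from baseline, so a subject's distance from an event is largely set before the first dose. When a strong predictor is left out of a Cox model, the estimated hazard ratio moves towards 1 even in a perfectly randomised trial, and power falls with it. Here the predictor is measured, defined and used in neighbouring models.

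The superiority claim on hypertension is at stake. Under the Protocol's order, so are the two endpoints behind it. Attenuation also touches the SAP's non-inferiority test, because a harmful hazard ratio is pulled towards 1 as well.

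**Working it through.** **1. The plan's own power figure.** The documents give no power for this endpoint. Their only figure is at least 99% for each primary endpoint with 600 subjects, and both reproduce at 300 per arm:
- Means: Φ(0.45 / (1.25 × √(2/300)) − 1.96) = Φ(4.41 − 1.96) = 99.3%, where 0.45 = 0.75 − 0.30.
- Proportions: Φ(0.15 / √(2 × 0.8 × 0.2/300) − 1.96) = Φ(4.59 − 1.96) = 99.6%.

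Neither bears on blood pressure.

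**2. Rise required by the definition alone.** Systolic rise = max(20, 170 − baseline):

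| Baseline systolic (mmHg) | 120 | 130 | 140 | 150 | 160 |
|---|---|---|---|---|---|
| Rise needed (mmHg) | 50 | 40 | 30 | 20 | 20 |

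Below 160 the level must be strictly exceeded, so each figure there means just over. The bend is at 170 − 20 = 150.

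**3. Visits.** Weeks 1-4 give 4, Weeks 6-24 every two weeks give 10, and Weeks 28-52 every four weeks give 7. That is 21 to Week 52, and 7 in the SAP's window. The Protocol states no end to its window; the calculations stop at Week 52.

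**4. How prognostic baseline is.** Visit-level pressures were simulated with both limbs of the event. Assumed: mean systolic 145, between-subject SD 15, visit SD 12. Event risk by baseline systolic quintile, lowest to highest:
- 7 visits: 4%, 12%, 25%, 35%, 31%.
- 21 visits: 10%, 25%, 46%, 58%, 52%.

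Over all the distributions tried, the ratio of peak to lowest quintile runs from about 3 (70/22) to about 9 (35/4). The fitted hazard ratio per SD of baseline systolic pressure is 1.33-1.63. Risk levels off at the top, as step 2 predicts.

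**5. What adjustment gains.** The measure is the ratio of squared Wald statistics, (log HR adjusted / log HR unadjusted)² × (SE unadjusted / SE adjusted)². It can be read as the equivalent increase in events. For N = 1000 with the step 4 distribution and a 3 mmHg effect, adding linear systolic and diastolic terms gives:
- 21 visits: (ln 0.700 / ln 0.713)² × (0.118/0.118)² = (0.3567/0.3383)² = 1.11. Power goes from 81.8% to 85.5%.
- 7 visits: (ln 0.682 / ln 0.690)² × (0.154/0.154)² = (0.3827/0.3711)² = 1.06. Power goes from 68.0% to 71.0%.

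The gain comes from the hazard ratio moving away from 1; the standard error hardly changes.

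Results across four sets of assumptions (gain in squared statistic):

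| Assumed inputs | 21 visits, linear | 21 visits, slope change at 150 | 7 visits, linear | 7 visits, slope change at 150 |
|---|---|---|---|---|
| Mean 140-150, between SD 12-18, visit SD 12-14, effect 2-3 mmHg, N = 600 or 1000 | 8-11% | not run | 4-7% | not run |
| Mean 140 or 145, SD 18 and 12, effect 2.5, 25% dropout, N = 600 or 1000 | 8-16% | 16-26% | 5% | 8% |
| Mean 142-145, SD 18 and 12, effect 2.5 | 17% | 26% | 3-4% | 6-9% |
| Mean 143, effect 2.5 (overall range) | 19-33% | (same range) | 6-14% | (same range) |

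In the first row's 16 scenarios the power gain runs from 0.8 points (21.7% to 22.5%) to 4.7 points (60.8% to 65.5%). With the slope change, gains in the second row are 4 to 9 points; the 9 is N = 600 over 21 visits, 52% to 61%.

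**6. Closed-form check (Schoenfeld).** With 180 events and HR 0.70, power = Φ(√(180/4) × 0.3567 − 1.96) = 66.7%. With 5% more events it is 68.9%, and with 10% more, 70.9%.

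**7. Validity.** With no treatment effect (7 visits, N = 1000), one-sided rejection was 1.6% unadjusted and 1.9% adjusted, against a nominal 2.5%.

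**The case against.** The best defence is that nothing is broken. The unadjusted test holds its level, and the gain is small in the window the SAP uses. In the third set of runs (7 visits, N = 1000) power moved only from 54% to 54-56% and from 64% to 65-66%. All of this stands.

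The plan also follows a convention by model type. Its Cox models (Protocol 8.4.3.2 and 8.4.3.3; SAP 11.2.1.6, 11.3.1.1 and 11.3.2) use stratification factors alone, while baseline values enter the MMRM, ANCOVA and logistic models. So this is not a slip in one model. But a convention that does no harm for hospitalisation is costly where the event is defined by change from baseline.

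Chance imbalance is a weak argument for adjusting. At 500 per arm a typical difference is √(2/500) = 0.06 SD, which at a hazard ratio of 1.3-1.6 per SD moves the log hazard ratio by 0.02-0.03.

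Nor does adjustment help non-inferiority. With no true difference over 7 visits, success against 1.3 was 41% unadjusted and 38-40% adjusted. With a true 2.5 mmHg harm the mean hazard ratio was 1.32 unadjusted and 1.37 with the slope change. This is a reason to say which scale the margin is on, not a reason to leave the covariate out.

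**Conclusion.** The point holds as a modest, inexpensive loss of efficiency in one secondary endpoint. Adding baseline pressure raises the squared statistic by about 8-33% over 21 visits and about 3-14% over Weeks 28-52, usually 1 to 5 power points. The dependence of risk on baseline follows from the event definition. The percentages rest wholly on assumed means, SDs and effects, because the documents give none.

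A reader might infer three stronger things that the documents do not support:
- **That the test is invalid or badly underpowered.** Type I error is not inflated, and the loss is modest.
- **That a miss always stops later tests.** It blocks MAP and time to first Hb response in the Protocol's order. In SAP Table 5 nothing follows, so only the hypertension claim is affected.
- **That the IV iron model has the same fault**, because SAP 11.2.1.4 uses an "ANCOVA model adjust for baseline iron replete" flag. The documents do not give the share of subjects who are not replete. Protocol 4.1 admits subjects below the ferritin or TSAT limits after supplementation without a retest, so it cannot be said that the flag varies little.

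**What to change.** In Protocol 8.4.3.2 and SAP 11.2.1.6, prespecify baseline systolic and diastolic pressure (SAP 5.4 definition) as continuous covariates in the Cox model. Let the systolic slope change at 150 mmHg, with terms for baseline and for max(baseline − 150, 0).

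State that the hazard ratio is conditional on baseline pressure and that the SAP's non-inferiority margin is applied to it. The margin must first be reconciled: Table 5 gives 1.8 and section 11.2.1.6 gives 1.3. The diastolic threshold also differs (110 in SAP 4.3 and Table 5, 100 in 11.2.1.6), as does the use of strict or non-strict inequality. The 150 mmHg bend does not depend on either.

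The cost is wording and three model terms, with no new data. The one downside is the conditional reading of the hazard ratio. Because the study is open-label, the change should be fixed before outcomes are compared by arm.

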#### 8.4.3.3 Additional Efficacy Analyses

- Hemoglobin maintenance: The mean change in Hb averaged over 8 weeks of treatment at Weeks 28 to 52 without rescue therapy within 6 weeks prior to and during this 8-week evaluation period. The mean change in Hb will be analyzed using an MMRM model with baseline Hb as a covariate and treatment group, visit, visits by treatment arm, and randomization stratification factors as fixed effects. Non-inferiority between roxadustat compared with epoetin alfa will be declared if the lower bound of the two-sided 95% CI of the difference between roxadustat and epoetin alfa exceeds -0.75 g/dL. All subjects will be included in the analysis
- HRQoL benefit of roxadustat will be assessed using SF-36 vitality and physical functioning subscales. Change from baseline at Weeks 12, 36, and 52 will be computed for each treatment group. A paired t-test will be used to assess within treatment effect. Between treatment difference will be assessed using an MMRM model with baseline subscore as a

covariate and treatment group visit, visits by treatment arm, and randomization stratification factors as factors. Noninferiority of roxadustat vs. epoetin alfa will be tested. The non-inferiority margin is fixed as a difference of 2 points.

The additional efficacy analyses will use the FAS population.

Additional efficacy analyses of continuous endpoints will use an MMRM model with baseline value, visit, visits by treatment arm, and randomization stratification factors as covariates.

Additional efficacy analyses of proportions will use the CMH model adjusting for treatment group and randomization stratification factors.

Additional efficacy analyses of time-to-event endpoints will use the Cox Proportional Hazards model adjusting for treatment and randomization stratification factors.

#### **8.4.4 Safety Analyses**

Safety analyses will be performed using the Safety Population. Safety parameters include AEs, laboratory parameters, vital signs, ECG parameters, and PEs. For each safety parameter, the last assessment made prior to the first dose of study medication will be used as the baseline for all analyses of that safety parameter.

The analytical methods for the MACE endpoint, as well as other composite safety endpoints of interest, will be described in a region-specific pooled statistical analysis plan to reflect the nature of the pooling of these endpoints across comparable studies in the Phase 3 program and the region-specific safety endpoints.

##### **8.4.4.1 Adverse Events**

Adverse events will be coded using the Medical Dictionary for Regulatory Activities (MedDRA).

An AE (classified by preferred term) occurring during the Treatment Period will be considered a TEAE if it was not present prior to the first dose of study medication, or if it was present prior to the first dose of study medication but increased in severity during the Treatment Period. An AE that occurs more than 28 days after the EOT/ET visit date will not be counted as a TEAE.

The number and percentage of subjects reporting TEAEs in each treatment group will be tabulated by system organ class and preferred term; by system organ class, preferred term, and severity; and by system organ class, preferred term, and relationship. If more than one event occurs with the same preferred term for the same subject, the subject will be counted only once for that preferred term using the most severe and most related occurrence for the summarization by severity and by relationship to the study medication.

The overall distribution of TEAEs by severity and relationship to study medication will be summarized by treatment group.

The proportion of subjects with TESAEs, fatal SAEs (ie, events that caused death), and AEs leading to discontinuation of study medication will be summarized by SOC, preferred term and treatment group.

Treatment emergent adverse events of interest will also be reported in terms of incidence rate per PEY.

Listings will be presented of subjects with SAEs, subjects with AEs leading to discontinuation, and subjects who died.

